## 10.2. Appendix 2: Adverse Events: Definitions and Procedures for Recording, Evaluating, Follow-up, and Reporting

### Definition of AE

#### AE Definition

- An AE is any untoward medical occurrence in a patient or clinical study participant, temporally associated with the use of study intervention, whether or not considered related to the study intervention.
- An AE can therefore be any unfavorable and unintended sign (including an abnormal laboratory finding), symptom, or disease (new or exacerbated) temporally associated with the use of study intervention.
- For devices, an AE is defined in accordance with ISO 14155 as any untoward medical occurrence, unintended disease or injury, or untoward clinical signs (including abnormal laboratory finding) in study participants, users, or other persons, whether or not related to the investigational medical device. This definition includes events related to the investigational medical device or comparator and events related to the procedures involved except for events in users or other persons, which only include events related to investigational devices.
- For devices, disease signs and symptoms that existed prior to the study intervention are not considered AEs.

#### Adverse Device Effect

- An ADE is defined in accordance with ISO 14155 as an AE related to the use of a medical device. This definition includes any adverse events resulting from insufficient or inadequate instructions for use, deployment, implantation, installation, or operation, or any malfunction of the investigational medical device as well as any event resulting from use error (per ISO 62366) or from intentional misuse of the medical device.

#### AE of Special Interest

An AESI (serious or nonserious) is one of scientific and medical concern specific to the sponsor's study drug/device or program, which warrants ongoing monitoring and rapid communication by the investigator to the sponsor. Such an event might warrant further investigation in order to characterize and understand it.

There are no AESIs identified for the study interventions. AESIs pertaining specifically to impression cytology are identified in Section [8.6.7](#).

## Intranasal Tear Neurostimulator

**Events Meeting the AE/ADE Definition**

- Any abnormal laboratory test results (hematology, clinical chemistry, or urinalysis) or other safety assessments (eg, ECGs, radiological scans, vital signs measurements), including those that worsen from baseline, considered clinically significant in the medical and scientific judgment of the investigator (ie, not related to progression of underlying disease); for example:
  - The test result is associated with accompanying symptoms, and/or
  - The test result requires additional diagnostic testing or medical/surgical intervention, and/or
  - The test result leads to a change in study dosing (outside of any protocol-specified dose adjustments) or discontinuation from the study, significant additional concomitant drug treatment, or other therapy, and/or
  - The test result is considered to be an AE by the investigator or sponsor.
- Exacerbation of a chronic or intermittent pre-existing condition including either an increase in frequency and/or intensity of the condition
- New condition detected or diagnosed after study intervention administration even though it may have been present before the start of the study
- Signs, symptoms, or the clinical sequelae of a suspected drug-drug interaction
- Signs, symptoms, or the clinical sequelae of a suspected overdose of either study intervention or a concomitant medication. Overdose per se will not be reported as an AE/ADE or SAE/SADE unless it is an intentional overdose taken with possible suicidal/self-harming intent. Such overdoses should be reported regardless of sequelae.
- Lack of effectiveness or failure of expected pharmacological action per se will not be reported as an AE/ADE or SAE/SADE. Such instances will be captured in the effectiveness assessments. However, the signs, symptoms, and/or clinical sequelae resulting from lack of effectiveness will be reported as AEs/ADEs or SAEs/SADEs if they fulfil the definition of an AE/ADE or SAE/SADE.

## Intranasal Tear Neurostimulator

**Events NOT Meeting the AE/ADE Definition**

- Any clinically significant abnormal laboratory findings or other abnormal safety assessments that are associated with the underlying disease, unless judged by the investigator to be more severe than expected for the participant's condition. Merely repeating an abnormal test, in the absence of any of the above conditions, does not constitute an AE/ADE. Any abnormal test result that is determined to be an error does not require recording as an AE/ADE.
- The disease/disorder being studied or expected progression, signs, or symptoms (clearly defined) of the disease/disorder being studied, unless more severe than expected for the participant's condition
- Medical or surgical procedure (eg, endoscopy, appendectomy): the condition that leads to the procedure is the AE/ADE
- Situations in which an untoward medical occurrence did not occur (social and/or convenience admission to a hospital)
- Anticipated day-to-day fluctuations of pre-existing disease(s) or condition(s) present or detected at the start of the study that do not worsen

**Definition of SAE**

SAEs must meet both the AE criteria described above and the seriousness criteria listed below.

**An SAE is defined in accordance with ISO 14155 as an AE that:**

- a. **Led to death**
- b. **Led to serious deterioration in the health of the participant, that either resulted in:**
  1. A life-threatening illness or injury, or
  2. A permanent impairment of a body structure or a body function, or
  3. Inpatient or prolonged hospitalization, or
  4. Medical or surgical intervention to prevent life-threatening illness or injury or permanent impairment to a body structure or a body function
- c. **Led to fetal distress, fetal death, or a congenital abnormality or birth defect**

**Serious Adverse Device Effect:**

A SADE is defined in accordance with ISO 14155 as an adverse device effect that has resulted in any of the consequences characteristic of a serious adverse event.

## Intranasal Tear Neurostimulator

**Unanticipated Adverse Device Effect:**

An UADE is defined in accordance with 21 CFR 812.3 as any serious adverse effect on health or safety or any life-threatening problem or death caused by, or associated with, a device, if that effect, problem, or death was not previously identified in nature, severity, or degree of incidence in the investigational plan or application (including a supplementary plan or application), or any other unanticipated serious problem associated with a device that relates to the rights, safety, or welfare of participants.

**Recording and Follow-Up of AEs/ADEs and/or SAEs/SADES****AE and SAE Recording**

- When an AE/ADE or SAE/SADE occurs, it is the responsibility of the investigator to review all documentation (eg, hospital progress notes, laboratory reports, and diagnostics reports) related to the event.
- The investigator will then record all relevant AE/ADE or SAE/SADE information in the CRF.
- It is **not** acceptable for the investigator to send photocopies of the participant's medical records to Allergan in lieu of completion of the AE/ADE or SAE/SADE CRF page.
- There may be instances when copies of medical records for certain cases are requested by Allergan. In this case, all participant identifiers, with the exception of the participant number, will be redacted on the copies of the medical records before submission to Allergan.
- The investigator will attempt to establish a diagnosis of the event based on signs, symptoms, and/or other clinical information. Whenever possible, the diagnosis (not the individual signs/symptoms) will be documented as the AE/SAE.

**Assessment of Intensity**

MILD	A type of adverse event that is usually transient and may require only minimal treatment or therapeutic intervention. The event does not generally interfere with usual activities of daily living.
MODERATE	A type of adverse event that is usually alleviated with additional specific therapeutic intervention. The event interferes with usual activities of daily living, causing discomfort but poses no significant or permanent risk of harm to the research participant.
SEVERE	A type of adverse event that interrupts usual activities of daily living, or significantly affects clinical status, or may require intensive therapeutic intervention.

## Intranasal Tear Neurostimulator

An event is defined as *serious* when it meets at least one of the predefined outcomes as described in the definition of an SAE/SADE, NOT when it is rated as severe.

**Assessment of Causality**

Every effort will be made by the investigator to assess the relationship of the AE, if any, to the device and/or study procedure. Causality should be assessed using the categories presented below:

- Not related: Clinical event of which the relationship to the device and/or procedure can be excluded, such as if the event is incompatible time relationship to study procedure and/or use of the device, involves a body part or organ not expected to be affected by the device or procedure, could be explained by underlying disease or other drugs or chemicals or is incontrovertibly not related to the study device, and is not due to use error.
- Unlikely: Clinical event whose time relationship to use of the device and/or study procedure makes a causal connection improbable, but that could plausibly be explained by underlying disease or other drugs or chemicals.
- Possible: Clinical event with a reasonable time relationship to the use of the device and/or study procedure, but that could also be explained by concurrent disease or other drugs or chemicals. Cases where relatedness cannot be assessed or no information has been obtained should also be classified as possible.
- Probable: Clinical event with a reasonable time relationship to the use of the device and/or study procedure, and is unlikely to be attributed to concurrent disease or other drugs or chemicals.
- Causal relationship: Clinical event with plausible time relationship to the use of the device and/or study procedure, is a known side effect of the product category the device belongs to or of similar devices and procedures; follows a known response pattern to the medical device; involves a body-site or organ that the device or procedures are applied to and/or influence; harm is due to error in use, and that cannot be explained by concurrent disease or other drugs or chemicals.

[REDACTED]  
Intranasal Tear Neurostimulator

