### **9.4.2. Safety Analyses**

The safety analysis will be performed using the safety population. The numbers and percentage of participants reporting AEs will be tabulated regardless of causality. Frequency of device and procedure related AEs, as well as AESIs will be summarized.

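### The causality scale lists a merely possible alternative cause as an example of Not related, which contradicts that category's own condition and overlaps with Possible and, in wording, Unlikely

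*Protocol*

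**What the plan says.** Protocol Appendix 2, Assessment of Causality, asks the investigator to "assess the relationship of the AE, if any, to the device and/or study procedure" and offers five categories: *Not related*, *Unlikely*, *Possible*, *Probable* and *Causal relationship*. Three of them mention an alternative cause.

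- *Not related* states its condition and goes straight into examples: "Clinical event of which the relationship to the device and/or procedure can be excluded, such as if the event is incompatible time relationship". The examples are alternatives. The later ones are that the event "could be explained by underlying disease or other drugs or chemicals or is incontrovertibly not related to the study device"; a closing rider rules out events caused by use error.
- *Unlikely* is an event whose timing "makes a causal connection improbable, but that could plausibly be explained by underlying disease or other drugs or chemicals".
- *Possible* is an event whose timing is reasonable, "but that could also be explained by concurrent disease or other drugs or chemicals". It is also the default when relatedness cannot be assessed.

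The rating is used in several places. Appendix 2 defines an adverse device effect (ADE) "as an AE related to the use of a medical device". Section 9.4.2 says "Frequency of device and procedure related AEs, as well as AESIs will be summarized", and also tabulates all adverse events (AEs) whatever their cause. Section 9.4.2.1 summarises treatment-emergent AEs and ADEs (TEAEs, TEADEs) by relationship to the study intervention.

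**The concern.** A causality scale works only if an event with given features has one right category. Here the features that define *Possible* (fitting timing, another cause available) also satisfy a listed example of *Not related*. Every participant has dry eye disease, so for an ocular complaint another cause is nearly always at hand. Two careful investigators, or one investigator on two days, could rate the same event at opposite ends of the related/unrelated divide, and both could point to the protocol text.

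At stake is the content of the relatedness, ADE and TEADE tables. Special-interest status may also be affected, because Section 8.6.7 defines adverse events of special interest (AESIs) as events related specifically to impression cytology, which is itself a judgement about cause.

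**Working it through.** No stated figure underlies this point, so the check is a comparison of texts.

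**Step 1: the example against its own condition.** The condition for *Not related* is that a relationship is excluded. The example is that another cause could explain the event. The second does not imply the first, because an event can have a candidate alternative cause and still be due to the device or procedure. The other examples do support exclusion: incompatible timing, an organ not expected to be affected, and an event incontrovertibly unrelated to the device. The alternative-cause example is the odd one out.

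**Step 2: the three categories side by side.**

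| Category | Timing | Alternative cause |
|---|---|---|
| *Not related*, by the example in question | no requirement | could explain the event (underlying disease, drugs, chemicals) |
| *Unlikely* | makes a causal link improbable | could plausibly explain it (underlying disease, drugs, chemicals) |
| *Possible* | reasonable | could also explain it (concurrent disease, drugs, chemicals) |

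An event with reasonable timing and a candidate alternative cause meets row 3 and the example in row 1. An event with improbable timing and a plausible alternative cause meets row 2 and the example in row 1. *Possible* speaks of concurrent rather than underlying disease, but in this study dry eye disease is both.

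**Step 3: whether such an event can arise here.** Sections 2.2 and 2.3 list discomfort, burning, grittiness and pain among dry eye symptoms. Section 8.6.7 lists discomfort (foreign body sensation, pain) as an AESI. Appendix 2 keeps expected symptoms of the studied disease from being recorded as AEs, with an exception for those more severe than expected for that participant. Ocular discomfort after cytology at the Application Visit, worse than the participant's usual dry eye, passes that filter, has reasonable timing and has dry eye as a candidate cause. It can be rated *Not related* or *Possible*.

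**Step 4: outputs that change.**

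- Affected: the device- and procedure-related AE summary (Section 9.4.2), the summary by relationship and the TEADE tables (Section 9.4.2.1), and possibly AESI status (Section 8.6.7).
- Not affected: the all-cause AE tabulation (Section 9.4.2) and the primary endpoint.

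**Step 5: weight of one participant.** Section 9.2 plans 24 intranasal and 12 extranasal participants. One participant moving between unrelated and related shifts the group percentage by 1/24 = 4.2 points or 1/12 = 8.3 points.

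**Step 6: device and procedure.** The scale is worded for device and/or procedure, whereas an ADE depends on the device alone. Section 4.1 places impression cytology after stimulation at the same visit, so timing separates the two causes poorly. The causality text does not require one rating for each.

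**The case against.** The best defence is that the opening condition of *Not related* governs its examples. On that reading an alternative cause counts only when it excludes a relationship, and a well-timed event belongs under *Possible*, which is also the default when relatedness cannot be assessed. This probably is the intent, and it narrows the overlap. It does not remove it: the example as written is weaker than exclusion, and a rater who relies on it is following the text.

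Second, the disease-symptom filter in Appendix 2 removes most dry eye complaints before they reach the scale, and the most frequent ADEs named in Section 2.3 are nasal, which dry eye would not explain. Both points stand. They confine the problem mainly to ocular events worse than expected.

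Three stronger readings are tempting, and the protocol does not support them.

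- *A reader might infer that events vanish from the safety reporting.* They do not: all AEs are tabulated irrespective of cause, and AEs and ADEs are listed.
- *A reader might infer that device and procedure must share one rating, so that cytology reactions become ADEs.* The and/or wording permits two ratings, and the case report form is not shown. Sections 9.4.2 and 9.4.2.1 and the ADE definition already speak of device, procedure or intervention separately. Appendix 7 asks for the relationship to the device when incidents are reported. Cytology at Screening precedes any application, so reactions to it cannot be device effects. What remains is that separate ratings are not required.
- *A reader might take 4.2 or 8.3 points as an expected error.* They are reciprocals of group size and say nothing about how often misclassification would occur.

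**Conclusion.** The point holds as an internal contradiction in one example of *Not related*, which makes that category overlap with *Possible* and with the alternative-cause wording of *Unlikely*. Its reach is limited to the classification of some events, chiefly ocular ones, in the relatedness and ADE/TEADE tables and possibly in AESI status.

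The size cannot be estimated from the protocol; only the weight of a single participant can be stated. The conclusion assumes that some ocular AEs occur that are more severe than the participant's expected dry eye. For the ADE/TEADE tables it also assumes that a rating of *Possible* counts as related and *Not related* does not. The lack of a requirement for separate device and procedure ratings is a secondary matter of clarity, not an error.

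**What to change.** In Appendix 2, Assessment of Causality, delete the alternative-cause example from *Not related*, or restrict it to cases where the other cause excludes a relationship to the device and procedure. Either way, an event with reasonable timing and only a possible alternative cause would be rated at least *Possible*. Deleting the example also removes the overlap in wording with *Unlikely*, which is then set apart by its timing condition.

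As a secondary clarification, add a sentence saying that the scale is applied once to the device and once to the study procedure, and that ADE and TEADE status follows from the device rating.

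The cost is a few lines of protocol text and, if the case report form does not already hold two ratings, one more field. Counts of related events may come out slightly less favourable. The change is best made before events are rated, because an analysis plan cannot restore a distinction that was not recorded.

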### Reporting of SAEs/SADEs

#### SAE/SADE Reporting to Allergan

- All SAEs/SADEs that occur from the time the ICF is signed through to their final study visit must be entered into the CRF and reported to the sponsor.
- Notify the sponsor immediately (within 24 hours) by fax using the Serious Adverse Event/Adverse Event of Special Interest Form for Devices.  
[REDACTED]

Intranasal Tear Neurostimulator

### 10.3. Appendix 3: Abbreviations

Abbreviation/Term	Definition
ADE	adverse device effect
AE	adverse event
AESI	adverse event of special interest
CAM	Cornea-Anterior Module
CDISC	Clinical Data Interchange Standards Consortium
CDVA	corrected distance visual acuity
CFR	Code of Federal Regulations
CI	confidence interval
CRF	case report form
DED	dry eye disease
ECG	electrocardiogram
ETDRS	Early Treatment Diabetic Retinopathy Study
FDA	Food and Drug Administration
FSH	follicle-stimulating hormone
GCP	Good Clinical Practice
HIPAA	Health Insurance Portability and Accountability Act
HRT	hormonal replacement therapy
IB	Investigator's Brochure
ICF	informed consent form
ICH	International Council for Harmonization
IEC	independent ethics committee
IRB	institutional review board
ISO	International Organization for Standardization
ITN	intranasal tear neurostimulator
ITT	intent-to-treat
LED	light-emitting diode
LFU	lacrimal functional unit
logMAR	logarithmic minimum angle of resolution
MedDRA	Medical Dictionary for Regulatory Activities
NCI	National Cancer Institute
NEI	National Eye Institute
OCT	optical coherence tomography
OSDI	Ocular Surface Disease Index
OTC	over-the-counter

## Intranasal Tear Neurostimulator

Abbreviation/Term	Definition
PT	preferred term
SADE	serious adverse device effect
SAE	serious adverse event
SAP	statistical analysis plan
SOC	system organ class
TEADE	treatment-emergent adverse device event
TEAE	treatment-emergent adverse event
TESADE	treatment-emergent serious adverse device advent
TESAE	treatment-emergent serious adverse event
TMH	tear meniscus height
UADE	unanticipated adverse device effect
WOCBP	women of childbearing potential

Intranasal Tear Neurostimulator

#### 10.4. Appendix 4: Standard Discontinuation Criteria

CDISC Submission Value	CDISC Definition
Adverse event	Any untoward medical occurrence in a patient or clinical investigation subject administered a pharmaceutical product and which does not necessarily have a causal relationship with this treatment. An adverse event (AE) can therefore be any unintended sign (including an abnormal laboratory finding), symptom, or disease temporally associated with the use of a medicinal (investigational) product, whether or not related to the medicinal (investigational) product. For further information, see the ICH Guideline for Clinical Safety Data Management: Definitions and Standards for Expedited Reporting (modified from ICH E2A) Synonyms: side effect, adverse experience. See also serious adverse event, serious adverse experience. (CDISC glossary)
Completed	To possess every necessary or normal part or component or step; having come or been brought to a conclusion (NCI)
Death	The absence of life or state of being dead (NCI)
Disease relapse	The return of a disease after a period of remission
Failure to meet randomization criteria	An indication that the subject has been unable to fulfill/satisfy the criteria required for assignment into a randomized group
Lack of efficacy	The lack of expected or desired effect related to a therapy (NCI)
Lost to follow-up	The loss or lack of continuation of a subject to follow-up
Non-compliance with study drug	An indication that a subject has not agreed with or followed the instructions related to the study medication (NCI)
Other	Different than the one(s) previously specified or mentioned (NCI)
Physician decision	A position, opinion or judgment reached after consideration by a physician with reference to subject (NCI)
Pregnancy	Pregnancy is the state or condition of having a developing embryo or fetus in the body (uterus), after union of an ovum and spermatozoon, during the period from conception to birth. (NCI)
Progressive disease	A disease process that is increasing in extent or severity (NCI)

